6.2.3.2 Laboratory assessments

For all laboratory parameters, the minimum and the maximum values on treatment (see Section 6.2) will be defined.

In addition, each laboratory result will be classified as low (L), normal (N), or high (H) at each visit according to the laboratory supplied reference ranges.

Change from baseline will be calculated as the measurement taken at the specific visit minus the measurement at baseline visit.

Baseline is defined as the assessment on Day 1 (prior to dosing), except for Hb (see Section 6.1.1.1). If Day 1 is missing, the screening or unscheduled assessment (prior to dosing) that is closest to Day 1 will be used.

Screening is defined as the screening or unscheduled assessment (during screening) that is closest to Day 1.

For the lipid panel and glucose parameter, two baseline values will be defined based on fasting status: regardless of fasting and fasted.

6.2.4 Physical Examination

A comprehensive physical examination will be conducted during the screening period and at the EOT visit and recorded in the source documents. This examination will include general appearance and the following body regions and systems: head, eyes, ears, neck and throat

(HEENT), lungs, heart, chest and back, abdomen, genitourinary, extremities, skin and any other, if deemed necessary.

A targeted examination (e.g., respiratory and cardiovascular) will be conducted and recorded in the source documents.

Only the date of the physical examination will be recorded in the eCRF. There will be no table or listing for the physical examination. Any clinically relevant adverse change will be recorded as an AE in the eCRF.

6.2.5 12-lead Electrocardiogram (ECG)

The 12-lead ECG measurements will be performed on all subjects at specific times. A single ECG measurement will be taken with the subject in the supine position, after the subject has been lying quietly for 5 minutes. Clinically significant abnormalities will be reported as an AE.

The visit, ECG date, Pulse, RR Interval, PR interval, QRS Interval, QT Interval, overall interpretation and relevant comments will be recorded in the eCRF.

Baseline assessment is the assessment from day 1 visit. If day 1 assessment is missing, screening period assessment will be used in the analysis.

QTc interval will be calculated using both

- Bazett ($QTcB = QT / (RR \text{ Interval})^{1/2}$) and
- Fridericia ($QTcF = QT / (RR \text{ Interval})^{1/3}$) corrections,

where QT is in msec and RR Interval in seconds; and if RR Interval is not available, it will be replaced with 60/HR.

For all ECG parameters, the maximum post-baseline value on treatment will be defined (see Section 6.2).

The QTc interval will be categorized at baseline and at each treatment visit using the range criteria defined in Table 9 below. This will be done for both Bazett and Fridericia correction formulas. The QTc interval changes from baseline will be categorized at each visit using the criteria defined in Table 9 below:

ECG values are potentially clinically significant (PCS) if they meet or exceed the upper limit values listed in Table 9 below.

Table 9 QTc Interval Classification

ECG Parameter	Classification
QTc interval (msec)	> 450 msec, > 480 msec, > 500 msec
QTc interval change (msec)	> 30 msec and > 60 msec

QRS and PR interval will also be categorized at baseline and at each treatment visit as defined in Table 10 below:

Table 10 Other ECG Parameters Classification

ECG Parameter	Classification
QRS (msec)	≥ 150 msec
PR (msec)	≥ 250 msec

Time to occurrence of PCS ECG:

For the two QTc criteria (QTc > 500 msec; change from baseline in QTc > 60 msec), the time to occurrence (in years) for a subject with occurrence of the PCS at any moment during Safety Emergent Period (defined in Section 6.2) will be calculated (in years) as defined in Section 6.2.2

Time to censoring will be defined as:

(Date of last ECG assessment where parameter analyzed is non-missing during the Safety Emergent Period – Analysis date of first dose intake +1) / 365.25

6.2.6 Vascular Access Thrombosis (VAT)

For each AE marked as VAT, additional information regarding the event will be listed.

Time to first VAT will be derived similarly to time to first occurrence of a TEAE, in Section 6.2.1.3 with first event date corresponding to the Date of first VAT. Censoring rules will be the same as without an event of interest.

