#### **Selection Criteria:**

##### *Inclusion*

Subject is eligible for the study if all of the following apply:

1. Institutional Review Board (IRB)-/Independent Ethics Committee (IEC)-approved written informed consent and privacy language as per national regulations has been obtained from the subject or legally authorized representative prior to any study-related procedures (including withdrawal of prohibited medication, if applicable).
2. Subject age is  $\geq 18$  years.

3. Subject is on stable HD, HDF or PD treatment with the same mode of dialysis for  $\geq 4$  months prior to randomization.
4. For subject receiving HD or HDF, the vascular access must be via native arteriovenous (AV) fistula or graft, or permanent, tunneled catheter.
5. Subject is on IV or SC epoetin (i.e. epoetin alfa, beta, theta, zeta, delta or omega) or IV or SC darbepoetin alfa treatment for  $\geq 8$  weeks prior to randomization with stable weekly doses ( $\leq 30\%$  change from the maximum prescribed average weekly dose, i.e.  $([\max - \min] / \max \leq 0.3)$  during 4 weeks prior to randomization. Subjects on polyethylene glycol-epoetin beta (Mircera®) are not to be included.
6. Mean of the subject's 3 most recent Hb values, as measured by central laboratory, during the screening period, obtained at least 4 days apart, must be  $\geq 9.5$  g/dL and  $\leq 12.0$  g/dL with an absolute difference  $\leq 1.3$  g/dL between the highest and the lowest value. The last Hb value must be within 10 days prior to the randomization visit (Day 1).
7. Subject has a ferritin level  $\geq 100$  ng/mL ( $\geq 220$  pmol/L) at screening.
8. Subject has a transferrin saturation (TSAT) level  $\geq 20\%$  at screening.
9. Subject has a serum folate level  $\geq$  lower limit of normal (LLN) at screening.
10. Subject has a serum vitamin B12 level  $\geq$  LLN at screening.
11. Subject's alanine aminotransferase (ALT) and aspartate aminotransferase (AST) are  $\leq 3$  x upper limit of normal (ULN), and total bilirubin (TBL) is  $\leq 1.5$  x ULN.
12. Subject's body weight (postdialysis weight) is 45.0 kg to a maximum of 160.0 kg.
13. Female subject is either:
  - Of non-childbearing potential:
    - postmenopausal (defined as at least 1 year without any menses) prior to screening, or
    - documented surgically sterile
  - Or if of childbearing potential:
    - agree not to try to become pregnant during the study and for 28 days after the final study drug administration.

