### 5.2.4 Diagnosis of the Target Disease, Severity, and Duration of Disease

A detailed anemia and CKD history for each subject will be obtained at screening and recorded in the eCRF. This includes date of diagnosis and symptoms of anemia, the date of diagnosis of CKD, etiology, vascular access history, date of initiation of current and first dialysis and mode of current and first dialysis. Also the nondrug therapy history and medication history for anemia (last 12 months) and the nondrug therapy history for CKD (last 4 months) prior to randomization will be obtained.

Anemia will be measured by repeated Hb measurements (central laboratory assessment) during screening; the mean of the 3 most recent Hb values during the screening period, obtained at least 4 days apart, must be  $\geq 9.5$  g/dL and  $\leq 12.0$  g/dL, with an absolute difference of  $\leq 1.3$  g/dL between the highest and the lowest values. The last Hb value must be within 10 days prior to randomization.

Exclusion of other causes of anemia should be based on an integrated assessment of clinical and laboratory signs and symptoms as well as medical history.

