5.4 Safety Analysis Set (SAF)

The safety analysis set consists of all randomized subjects (All Randomized) who received at least one dose of study drug. Subjects will be assigned to their actual treatment received during the trial.

The SAF will be used to describe demographic and baseline characteristics and all safety and tolerability related variables.

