7.5 Analysis of Safety

Safety analyses will be performed using the Safety Analysis Set (SAF).

Missing dates' imputation rules for AE onset date and stop date are detailed in Section 7.11.2

For each safety parameter, the last non-missing assessment prior to the first dose of study drug will be used as the baseline for all analyses, unless specified otherwise.

For the safety analyses by subgroup, the subgroup analysis by Previous ESA treatment will not be presented in tables, as this analysis is already performed by Type of ESA treatment (Subgroup Darbepoetin and Subgroup Epoetin). In forest plots, results for this subgroup factor Previous ESA treatment will be included.

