7.5.1.4 Incidence Rates and Cumulative Incidence

Since the percentage of adverse events might be different between treatment arms due to the difference in the discontinuation rates, in addition to the frequency tables above, the incidence rate (per 100 subject years at risk) and the cumulative incidence at 0.5 year, 1 year, 1.5 years & 2 years with the 95% confidence interval, using Greenwood's formula, will be reported by treatment arm and type of ESA treatment.

It will be done for each of the following event types of special interest:

- Serious TEAEs,
- Deaths occurring during the Safety Emergent Period,
- All deaths during study period and post study safety follow up period,
- Related serious TEAEs,
- TEAEs leading to discontinuation of study drug, and
- TEAE NCI CTC Grades 3 or higher.

Hazard ratios of each of the TEAE categories of special interest above will be computed by using Cox Proportional Hazards regression stratified on region, history of CV, previous ESA treatment and adjusted on baseline Hb as continuous covariate. Hazard ratios (roxadustat as relative to ESA) and their 95% CI will be calculated for each TEAE category.

A dot-and-forest plot will be produced showing each of the above TEAE category on the y-axis. The incidence rates by treatment arm, the stratified Cox hazard ratios (roxadustat as relative to ESA) and their 95% CI will be shown on the x-axis.

In addition, cumulative incidence plots for subjects experiencing each of the TEAE categories above will be produced by treatment arm and type of ESA treatment.

Incidence rate (per 100 subject years at risk) for most common PT ($\geq 5\%$ in the total population) by SOC and the cumulative incidences of TEAE by SOC will also be produced for TEAEs in each treatment arm: Cumulative Incidence plots of subjects experiencing each SOC will be produced. A dot-and-forest plot will be produced showing each SOC in the y-axis and the incidence rates, the Cox hazard ratio and its 95% CI in the x-axis. The SOC will be sorted by the hazard ratio.

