7.5.5 Vascular Access Thrombosis (VAT)

Time to first VAT will be analyzed similarly as in Section [7.5.1.4](#) (Time to event analysis for TEAEs).

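### Vascular access thrombosis rates are computed on the whole safety set, so peritoneal dialysis follow-up counts as time at risk and dilutes them by about the peritoneal dialysis share

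*SAP*

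**What the plan says.** VAT was added as a specific safety analysis in SAP version 3.0 (SAP 8). It has no event-specific rules for who is at risk. SAP 6.2.6 says "Time to first VAT will be derived similarly to time to first occurrence of a TEAE", with the same censoring, and SAP 7.5.5 says "Time to first VAT will be analyzed similarly as in Section" 7.5.1.4. That section produces an incidence rate per 100 subject-years at risk, cumulative incidence at fixed times, and a Cox hazard ratio "stratified on region, history of CV, previous ESA treatment and adjusted on baseline Hb as continuous covariate".

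SAP 7.5 places all safety analyses on the SAF, which "consists of all randomized subjects (All Randomized) who received at least one dose of study drug", whatever the dialysis mode. A subject without the event is censored at the end of the Safety Emergent Period (SAP 6.2.1.3), and the rate's denominator sums everyone's time to event or censoring (SAP 6.2.1.4).

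Both HD/HDF and PD subjects are enrolled (SAP 3.2.2). The access criterion in the protocol synopsis covers only the former: "For subject receiving HD or HDF, the vascular access must be via native arteriovenous (AV) fistula or graft, or permanent, tunneled catheter". SAP 6.5.2 derives dialysis type as hemodialysis (including HDF) versus peritoneal dialysis. The footnote to Table 26 in SAP 7.8 keeps the dialysis-type subgroup for the primary Hb analyses.

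**The concern.** A rate per subject-year at risk should count the time of people who can have the event. For PD subjects the protocol requires no vascular access, so most of their follow-up is probably not time at risk of access thrombosis, yet it is counted in full. No planned VAT summary table separates the two dialysis modes.

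The SAP already applies the at-risk principle elsewhere. In SAP 7.5.2, incidence rates and cumulative incidences of potentially clinically significant laboratory abnormalities use only subjects who did not meet the criterion at baseline. VAT has no equivalent rule.

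The event is not incidental to this drug class. Protocol 1.3.3 names access thrombosis among the few events consistently reported as related to study drug in the darbepoetin program. Protocol 1.3.2 reports clotted access at 0.25 events per patient-year with epoetin, and more access thrombosis in the higher-target arm of an earlier epoetin trial. At stake is the absolute level of the reported rate, which readers will compare with figures of this kind.

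**Working it through.** The documents give no VAT rate, event count, power statement or PD share for this trial, so there is no planned figure to reproduce. The size has to be shown over assumed values.

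**Inputs**
- PD share p: assumed 5%, 10% and 15%. For reference, the US counts in Protocol 1.1.1 give 27,000 / (370,000 + 27,000) = 6.8%.
- VAT hazard λ in HD/HDF subjects: assumed constant at 0.05 to 0.25 per year. The upper value borrows the 0.25 events per patient-year in Protocol 1.3.2.
- Hazard in PD subjects: assumed zero, which gives the largest dilution.
- Follow-up T: 1.08 or 2.08 years (56 or 108 weeks, the shortest and longest planned treatment plus 4 weeks).

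**Cumulative incidence.** In HD/HDF subjects it is F = 1 − exp(−λT). On the whole SAF it is (1 − p)F, so it is too low by exactly p. With λ = 0.25 and T = 2.08, F = 40.5%. With p = 6.8% the SAF figure is 0.932 × 40.5% = 37.8%.

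**Incidence rate.** In HD/HDF subjects it is λ. On the whole SAF it is (1 − p)F / [(1 − p)F/λ + pT]. With λ = 0.25, T = 2.08 and p = 10%: numerator 0.90 × 0.4055 = 0.365; denominator 0.90 × 1.622 + 0.10 × 2.08 = 1.668; rate 21.9 per 100 subject-years against 25.0, which is 12.5% too low. The shortfall slightly exceeds p because PD subjects are never removed by an event.

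| Assumed PD share | Rate too low, λ = 0.05, T = 1.08 | Rate too low, λ = 0.25, T = 2.08 | Cumulative incidence too low |
|---|---|---|---|
| 5% | 5.1% | 6.3% | 5% |
| 10% | 10.2% | 12.5% | 10% |
| 15% | 15.3% | 18.5% | 15% |

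**Hazard ratio.** The population Cox score equation was solved with zero-hazard PD subjects kept in the risk sets, λ = 0.10 and 0.25, T = 2.08. With equal PD shares in the arms (6.8%, 10% or 20%), a true hazard ratio of 1.00 stays 1.00, and a true 1.30 becomes 1.28 to 1.30.

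**Unequal shares.** Dialysis mode is not among the five randomization factors (SAP 3.3), so shares can differ by chance. At p = 10% and 375 per arm, the SD of the difference is √(2 × 0.10 × 0.90 / 375) = 0.022. Divided by 0.90, this is about 0.024 on the log hazard ratio. For comparison, assume 700 HD/HDF subjects and λ = 0.25. First events number about 700 × 0.237 = 166 to 700 × 0.405 = 284, so the SE of the log hazard ratio (2/√events) is 0.155 to 0.119. Adding 0.024 in quadrature raises that SE by only 1% to 2%.

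**The case against.** A whole-SAF rate is a legitimate description of all treated subjects, as used for every other adverse event, and *too low* presumes a different target population. That is fair, but the output is labelled as time at risk, and for this one event that label does not fit subjects without an access. The whole-SAF figure is still worth keeping alongside.

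The documents do not say that PD subjects have no access. The criterion states what HD/HDF subjects need. Protocol 5.2.4 records vascular access history and the mode of both first and current dialysis, and a change of dialysis mode is not listed among the discontinuation reasons in Protocol 6.1. Some PD subjects may have an earlier or back-up access or move to HD. This stands: the zero hazard is an upper bound on the dilution, and an HD/HDF-only analysis needs a separate listing of PD events.

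Dilution is also partly recoverable. Each VAT is listed with further details, and dialysis type is tabulated at baseline (SAP 7.2.3), so a reader could rescale the cumulative incidence. What is missing is a planned VAT result for HD/HDF subjects.

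Two stronger inferences are tempting and are not supported:

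- *The hazard ratio is biased by chance imbalance in PD share.* Such imbalance is ordinary sampling error, which the confidence interval already covers, and it is small beside the standard error. A split of 4% versus 10% would turn a true 1.00 into 1.07 to 1.08. But at 6.8% PD the SD of the difference is 0.018, so a gap of 0.06 is about a 3-SD event.
- *Access type is already recorded and belongs in the Cox model.* Protocol 5.2.4 mentions only access history, and SAP 6.5.2 uses vascular access only for time since diagnosis. A coded fistula, graft or catheter variable is an inference, and the documents give no shares or relative risks by access type.

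**Conclusion.** The point holds for absolute measures. As planned, VAT incidence rates and cumulative incidences include follow-up of PD subjects, for whom no vascular access is required, and are understated for HD/HDF subjects by about the PD share or slightly more. For an assumed share of 5% to 15%, this is 5% to 15% for cumulative incidence and about 5% to 18% for the rate. These sizes rest on an assumed PD share, a constant hazard and no events in PD subjects; any VAT in PD subjects makes the dilution smaller. The dilution is the same in expectation in both arms, so the treatment comparison is essentially intact. No primary or key secondary conclusion depends on it. This is a cheap improvement to a named safety analysis and does not threaten the trial's conclusions.

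**What to change.** In SAP 6.2.6 and 7.5.5, define the main VAT analysis as SAF subjects on HD/HDF at baseline, using the dialysis-type variable in SAP 6.5.2, which takes the latest mode before first dosing. Report the incidence rate, cumulative incidence and Cox hazard ratio in that set, with the model otherwise as in SAP 7.5.1.4. Keep the whole-SAF result as a sensitivity analysis. List any VAT in PD subjects separately, so that events in those with an existing access or a switch to HD stay visible.

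The cost is a slightly smaller denominator and one extra set of outputs. No new data are needed, because the flag is already derived.

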6.3 Pharmacokinetic Variables

All details of the population PK analysis will be described in a separate analysis plan.

6.4 Pharmacodynamic Variables

Not applicable.

6.5 Other Variables

6.5.1 Eligibility criteria

Eligibility at screening will be recorded as a yes/no variable for each criterion. The date of the informed consent for the subjects will also be documented.

6.5.2 Demographic and Baseline Characteristic Variables

Demographic characteristics will be recorded at screening (sex, the day, month and year of birth, age, race, height and weight).

Collection of date of birth depends on local regulations. Day of birth will be recorded in the eCRF as the first of the month when the day is not allowed to be collected. In cases where only year of birth is allowed to be collected, day and month will be recorded in the eCRF as the first of January. Age will be recalculated in SDTM and ADaM datasets.

Age at baseline is calculated as $\text{Age} = (D_{\text{First}} - D_{\text{B}}) / 365.25$, with D_{B} as the Date of Birth and D_{First} as the Date of First Dose intake. If the Date of First Dose intake is not available, the Date of Informed Consent will be used.

Based on recalculated age, three categories will be defined:

- < 65 years,
- 65 - 74 years,
- ≥ 75 years

Each subject's body mass index (BMI) will be calculated as:

$$\text{BMI (Kg/m}^2\text{)} = \text{Weight (Kg)} / [\text{Height (m)}]^2,$$

in which the height will be converted from cm. into m. by dividing by 100.

Tobacco history and use will be recorded at screening.

The average maximum quantity of tobacco per week will be calculated using the average maximum quantity and frequency filled in the CRF. If the frequency is "Day", the average maximum quantity of tobacco per week will be determined as follows:

$$\text{average maximum quantity per day} \times 7$$

If the frequency is "/Month", the average maximum quantity of tobacco per week will be determined as follows:

$$\text{average maximum quantity per month} / 4.3482$$

Screening Hb will be defined as the mean of the three latest central laboratory Hb values prior to the day of randomization.

Baseline Hb is defined in Section [6.1.1.1](#)

Based on the mean screening Hb value, two categories will be defined:

- ≤ 11.0 g/dL
- > 11.0 g/dL

History of cardiovascular, cerebrovascular or thromboembolic diseases at baseline will be defined for subjects with any of the diseases that have been reported in the Cardiovascular Disease History eCRF. History will be categorized as:

- Yes
- No

Countries and Regions

Subjects will be enrolled from the following 17 countries:

Region A (Western Europe)

- Belgium
- France

- Germany
- Italy
- Portugal
- Spain
- UK

Region B (Central and Eastern Europe)

- Bulgaria
- Croatia
- Hungary
- Poland
- Romania
- Russia
- Serbia
- Czech Republic
- Slovakia
- Georgia

Randomization will be stratified by region using two categories:

- Region A: Western Europe
- Region B: Central and Eastern Europe.

Time to Treatment Discontinuation

Time to Treatment Discontinuation in years is defined as:

Time to Treatment Discontinuation (years) = ('Date of Treatment Discontinuation' - 'Analysis date of first dose intake' + 1) / 365.25

In case a subject completed the treatment period, time to censoring will be calculated as:

$$(\text{EoT visit} - \text{Analysis date of first dose intake} + 1) / 365.25$$

Time in years from Diagnosis of Anemia

Time from diagnosis of anemia in years is defined as:

Time from Diagnosis of Anemia (years) = ('Analysis date of first dose intake' - 'Date of Diagnosis') / 365.25

In case of partial dates, imputation rules apply and are detailed in Section [7.11.2](#)

Time in years from Diagnosis of CKD

Time from diagnosis of CKD in years is defined as:

Time from Diagnosis of CKD (years) = ('Analysis date of First Dose intake' - 'Date of Diagnosis of CKD') / 365.25

In case of partial dates, imputation rules apply and are detailed in Section [7.11.2](#)

Time from Diagnosis of Targeted Medical History

Onset date and the start date of analysis for the study drug are collected and the time from diagnosis of targeted medical history in years is defined as

$$\text{Time from Diagnosis of Targeted Medical History (years)} = \frac{(\text{'Analysis date of first dose intake'} - \text{'Onset Date'})}{365.25}$$

In case of partial dates, imputation rules apply and are detailed in Section [7.11.2](#)

This will be calculated for each patient who was diagnosed with the targeted medical history: hypertension, diabetes mellitus type 1, type 2 and combined, dyslipidemia and vascular access.

Iron Repletion at Screening

Subjects will be classified in one of the following groups according to the TSAT and ferritin levels collected at Screening (prior to first drug intake):

- Ferritin <100 ng/mL and TSAT <20%
- Ferritin < 100 ng/mL and TSAT \geq 20%
- Ferritin \geq 100 ng/mL and TSAT <20%
- Ferritin \geq 100 ng/mL and TSAT \geq 20%
- Other

Iron Repletion at Baseline

Subjects will be classified in one of the following groups according to the TSAT and ferritin levels collected on Day 1:

- Ferritin <100 ng/mL and TSAT <20%
- Ferritin < 100 ng/mL and TSAT \geq 20%
- Ferritin \geq 100 ng/mL and TSAT <20%
- Ferritin \geq 100 ng/mL and TSAT \geq 20%
- Other

If no Day 1 assessment is available, Iron Repletion at Screening will be used.

Average weekly ESA dose before randomization.

All subjects randomized will be classified into two groups:

- Subjects with lower average weekly ESA dose prior to randomization (\leq 200 IU/kg epoetin or \leq 1 μ g/kg darbepoetin alfa), versus
- Subjects with higher average weekly ESA dose prior to randomization ($>$ 200 IU/kg epoetin or $>$ 1 μ g/kg darbepoetin alfa).

It will be derived using data in 'Treatment History of Anemia' eCRF. The methodology to derive the dose is described in Section [6.5.4](#)

Dialysis type

Dialysis type is recorded in the eCRF *Cumulative* form: *Dialysis method*. All subjects will be classified into two groups (if two types of dialysis are reported, the latest one prior to first dosing will be used):

- Hemodialysis subjects (including hemodiafiltration), versus
- Peritoneal dialysis subjects (continuous ambulatory and automated)

Previous ESA treatment.

In the form *Screening Procedures - Treatment history for Anemia and ESA Treatment history for Anemia*, if the variable 'Medication type'='ESA' and 'Specify type of ESA'='Darbepoetin Alfa' then the variable 'Previous ESA Treatment will be coded as 'Darbepoetin Alfa'.

For all other values, as there are several epoetin types, it will take the value 'Epoetin'.

